5.3. Discontinuation of Study Drug

A participant may choose to discontinue the study drug at any time for any reason. Reasons for discontinuation from study drug may include, but are not limited to, the following:

- Adverse event
- Pregnancy
- Investigator discretion
- Participant request

If a participant discontinues the study drug, the reason and date of discontinuation must be recorded. If STAR-0215 is discontinued, the participant should remain in the study to complete all follow-up visits and assessments as described in the SOAs ([Section 1.1](#)). Participants who become pregnant while participating in the study will be discontinued from STAR-0215 and followed for safety. Pregnancy reporting is described in [Section 8.5.1](#).

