8.2. Adverse Event Definitions

8.2.1. Adverse Event Definition

An adverse event (AE) is any untoward medical occurrence in a patient or clinical investigation participant administered a pharmaceutical product that does not necessarily have a causal relationship with this treatment. In clinical studies, an AE can include an undesirable medical condition occurring at any time, including baseline or washout periods, even if no study treatment has been administered.

Laboratory abnormalities are generally not considered AEs unless they are associated with clinical signs or symptoms or require medical intervention. A clinically significant laboratory abnormality that is independent from a known underlying medical condition and that requires medical or surgical intervention, or leads to study drug interruption or discontinuation, will be considered an AE.

If a participant experiences symptoms that support an HAE attack, those symptoms/attacks will not be reported as AEs. However, if those symptoms are not supportive of an HAE attack, they will be reported as AEs. Any HAE attack that meets the definition of an SAE ([Section 8.2.2](#)) will be captured as an SAE.

For participants who do not enroll in the long-term open label extension study, and experience HAE attacks after 6 months following the last dose of STAR-0215, those will be reported as AEs.

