9.4. Safety Analysis

9.4.1. Adverse Events Analysis

Adverse events will be coded using the Medical Dictionary for Regulatory Activities (MedDRA) Version 25.0 or higher and will be graded as described in Section 8.4.

Summaries of AEs will be based on treatment emergent AEs (TEAEs), defined as AEs with an onset at the time of or following the start of treatment with study drug, or medical conditions present before the start of treatment that increase in severity or relationship at the time of or following the start of treatment.

Treatment emergent AEs will be summarized separately for each dose level and by the number of participants experiencing TEAEs corresponding to MedDRA System Organ Classes (SOCs) and Preferred Terms (PTs) by highest grade.

Separate tabulations may also be produced for TEAEs assessed as related to study drug, TEAEs that led to treatment discontinuation, TEAEs that led to death, and TEAEs greater than or equal to Grade 3 in severity. Common AEs will be summarized by MedDRA PT from most to least common. Treatment emergent SAEs and treatment emergent SAEs related to study drug will also be tabulated.

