### 3 STUDY ENDPOINTS

#### 3.1 Primary Endpoints

- Incidence of adverse events (AEs)
- Change from Baseline in vital signs, electrocardiogram (ECG) findings, physical examination findings, and clinical laboratory evaluations

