### 6.6.1 Adverse Events

Adverse events will be coded using MedDRA and will be graded using the severity scale specified in the protocol. .

Summaries of AEs will be based on treatment emergent AEs (TEAEs), defined as AEs with an onset at the time of or following the start of treatment, or medical conditions present before the start of treatment that increase in severity or relationship at the time of or following the start of treatment.

Adverse events are summarized by participant, therefore, in any tabulation, a participant contributes only once to the count for a given adverse event (SOC or PT).

Separate tabulations may also be produced for TEAEs assessed as related to study drug (related, probable, or possible relationship), TEAEs that led to discontinuation from study, TEAEs that led to death, TEAEs greater than or equal to Grade 3 in severity and TEAEs by highest grade. Common AEs will be summarized by MedDRA PT from most to least common. Treatment emergent SAEs and treatment emergent SAEs related to study drug will also be tabulated.

No formal hypothesis-testing analysis of adverse events incidence rates will be performed.

All adverse events occurring on study will be listed in subject data listings.

By-subject listings also will be provided for the following: participant deaths; serious adverse events; and adverse events leading to study discontinuation.

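### SAP 6.6.1 drops the protocol's breakdown of AEs leading to treatment discontinuation without declaring it, and the TEAE definition has no end, so late HAE attacks count as TEAEs only in participants who do not roll over

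*SAP*

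**What the plan says.** **Discontinuation.** Protocol 9.4.1 lists, among tabulations that may be produced, "TEAEs that led to treatment discontinuation". The matching item in SAP 6.6.1 is "TEAEs that led to discontinuation from study". It is optional there too; the sentence opens "Separate tabulations may also be produced for TEAEs assessed as related to study drug". The SAP also commits, without the optional wording, to a by-subject listing of "adverse events leading to study discontinuation". Protocol 5.3 separates stopping drug from leaving the study: "If STAR-0215 is discontinued, the participant should remain in the study to complete all follow-up visits and assessments". SAP Section 7 states that, apart from the revised text tied to Section 2.5, the analyses are unchanged from the protocol.

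**TEAE window.** Protocol 9.4.1 and SAP 6.6.1 both define a TEAE by onset, or worsening, at or after the start of treatment. Neither gives an end. Under Protocol 8.2.1, HAE attacks are not reported as AEs unless they meet the SAE definition. The exception is participants who stay out of the extension study: if they "experience HAE attacks after 6 months following the last dose of STAR-0215, those will be reported as AEs". AE incidence is a primary endpoint (SAP 3.1).

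**The concern.** An AE that costs a participant the second dose is a basic tolerability result for a two-dose regimen. The protocol foresaw a table for it, and the SAP has a table and a listing for a different event. A reader who sees zero under study discontinuation could take it to mean that no AE stopped treatment.

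The second part concerns what the AE total measures. The same kind of attack is an efficacy event before the 6-month visit and, in some participants only, an adverse event after it. Two people with identical dosing and disease can then be counted differently on a primary safety endpoint because one entered STAR-0215-202 and the other did not.

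**Working it through.** The plan states no figure for either part, so there is none to reproduce. The check is a comparison of text, followed by a calculation of scale.

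**(a) Where would an AE that prevents Dose 2 appear?** Take a participant in Cohort 2 or 3 who has such an AE and completes follow-up.

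- SAP 6.6.1 discontinuation table: no, because the participant did not leave the study.
- SAP 6.6.1 discontinuation listing: no, for the same reason.
- SAP 6.3.1 disposition: no, because it counts completion and discontinuation of the study.
- SAP 6.3.3 dosing listing: yes, as a missing second administration, but not linked to an AE.
- Overall TEAE incidence and the listing of all AEs: yes.

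The SAP itself recognises treatment discontinuation as an event, since Section 6.2.6 makes such participants non-responders for binary endpoints. Protocol 8.5 has the investigator record, for each AE, the action taken and whether the AE led to leaving the study. The data may therefore exist.

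Participants in whom the event could occur are those in the two-dose cohorts: 6 + 6 = 12 of 16 initially (75%), and up to 12 + 12 = 24 of 28 (86%). The documents give no expected number of events.

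**(b) How do late attacks become TEAEs?** Protocol 8.2.1 makes them AEs. Their onset is after first dose, so they meet the TEAE definition. Recording runs to the final study visit (Schedules of Assessments), and Protocol 7.15 has the later contacts ask about HAE attacks. SAP 5.2 ends the treatment period at the Day 168, 251 or 195 visit, but for HAE assessments only. No SAP rule caps the TEAE window or separates these attacks. Depending on grade and the investigator's causality call, they could also enter the Grade 3 or higher and related tables.

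**Scale of (b).** Inputs from the documents: at least 2 attacks in a run-in of at least 56 days (Protocol 5.1 and 4.5), and 30.4375 days per month (SAP 5.2). The minimum eligible rate for a 56-day run-in is 2/56 × 30.4375 = 1.09 per month. An extended run-in would lower this minimum, and a participant's actual rate may be higher.

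Assumed inputs: 1, 3 or 6 further months of follow-up (the true length is redacted); attacks at 100%, 50% or 10% of 1.09 per month; Poisson occurrence. The chance of at least one late attack is 1 − exp(−rate × months):

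| Share of 1.09/month | 1 month | 3 months | 6 months |
|---|---|---|---|
| 100% | 66% | 96% | >99% |
| 50% | 42% | 80% | 96% |
| 10% | 10% | 28% | 48% |

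Incidence counts participants, so a late attack changes the overall figure only for someone with no other TEAE. With *k* of 28 not rolling over, a share *b* already having a TEAE, and probability *p* from the table (taken as independent of *b*), the rise is (k/28) × (1 − b) × p. For illustration, assume b = 50%:

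- k = 3, p = 0.962: 3/28 × 0.5 × 0.962 = 0.052, so 50% becomes about 55%.
- k = 6, p = 0.962: 6/28 × 0.5 × 0.962 = 0.103, so 50% becomes about 60%.
- k = 3, p = 0.103: 3/28 × 0.5 × 0.103 = 0.006, a rise of 0.6 points.

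One participant with no other TEAE moves a cohort of 4 by 25 points, a cohort of 6 by 17, and a cohort of 12 by 8.

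**The case against.** On (a), the discontinuation tabulation is optional in both documents and is only a supporting breakdown. An AE that stops drug still counts in overall TEAE incidence and in any SAE, Grade 3 or higher, or related table where it qualifies. All AEs and all administrations are listed, and with 16 to 28 participants a reader can work from listings. All of this stands. A reader might infer that the primary-endpoint tables are mis-specified, or that a tolerability signal is hidden; the documents do not support that. Nor are 24 of 28 participants affected: that is the number in whom the event could happen. What remains is a missing row and listing, and an inaccurate statement in Section 7.

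On (b), the open definition is in the protocol too, and Protocol 8.2.1 makes late attacks reportable on purpose, so the SAP has not departed from the protocol. Coded HAE terms can be picked out by preferred term. Protocol 2.4.1 says only that suppression may be lost after about 6 months, and Protocol 7.15 permits some HAE prophylaxis from then on, which could keep attack rates low. These points stand. They limit the size but do not remove the dependence on rollover status. A reader might also conclude that each late attack adds 25 or 17 points to a cohort's incidence, but that holds only for a participant with no other TEAE.

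Ending the whole TEAE window at the 6-month visit is also tempting. It would take out of the main incidence every AE from a period the protocol sets aside for safety monitoring, so it is a debatable trade-off and not a correction that the text requires.

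**Conclusion.** Both parts hold in limited form.

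(a) The SAP substitutes study discontinuation for treatment discontinuation in one optional table and pairs it with a listing of the same kind. AEs that stop STAR-0215 while follow-up continues have no discontinuation output, and the Section 7 statement is incorrect on this item. The events would be untabulated in that respect, but not lost.

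(b) This is a gap shared by protocol and SAP. HAE attacks later than 6 months after the last dose enter TEAE incidence in non-rollover participants only. The amount cannot be fixed from the documents, because the follow-up length is redacted and the number not rolling over is not given. The range of about 10% to over 99% per non-rollover participant rests on the assumed months, rates and Poisson model. The effect on overall incidence could be under 1 point or several points. Analyses are descriptive and no AE hypothesis is tested, so the consequence is for interpretation and not for an error rate.

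**What to change.** In SAP 6.6.1:

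1. Add a table row and a by-subject listing for TEAEs leading to discontinuation of STAR-0215, derived from the action-taken field in Protocol 8.5. First confirm that the CRF codes drug withdrawal there. Keep the study-discontinuation outputs alongside.
2. Put HAE attacks reported as AEs in their own row, and show TEAE incidence with and without them.
3. Tabulate AEs with onset after the Day 168, 251 or 195 visit separately, while keeping all AEs in the overall safety summary.

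In SAP Section 7, correct the statement that nothing else changed. Exposure-adjusted rates would help a reader compare cohorts with different follow-up, but they are optional.

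The cost is SAP wording, one listing and one or two tables. No new data are needed if the CRF already codes drug withdrawal.

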### 6.6.2 Laboratory Data

The actual value and change from Baseline to each post-baseline evaluation will be summarized for each clinical laboratory parameter, including hematology and clinical chemistry. In the event of repeat values, the last non-missing value per study day/time will be used.

All laboratory data will be provided in data listings.

A subset listing will be presented for all abnormal laboratory values.

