7.9. Clinical Laboratory Assessments

All clinical laboratory assays (hematology, chemistry, coagulation, and urinalysis) will be performed according to the central laboratory's normal procedures. Reference ranges are to be supplied by the laboratory and will be used to assess the clinical laboratory data for clinical significance and out-of-range pathological changes. The Investigator should assess out-of-range clinical laboratory values for clinical significance, indicating if the value(s) is/are not clinically significant or clinically significant. Abnormal clinical laboratory values that are unexpected or not explained by the participant's clinical condition may, at the discretion of the Investigator or Sponsor, be repeated as soon as possible until confirmed, explained, or resolved.

Clinical laboratory parameters are listed in [Table 7](#).

Table 7: Clinical Laboratory Parameters

Hematology	Chemistry	Coagulation	Urinalysis
CBC with differential: Hemoglobin Hematocrit RBC count Platelet count Mean corpuscular volume Mean corpuscular hemoglobin Mean corpuscular hemoglobin concentration WBC count with differential (lymphocytes, neutrophils, monocytes, eosinophils, and basophils)	Albumin Alkaline phosphatase ALT AST Bilirubin (total and direct) Blood urea nitrogen Calcium Carbon dioxide Chloride Cholesterol Creatine phosphokinase Creatinine Gamma-glutamyl transferase Glucose Lactate dehydrogenase Magnesium Phosphate Potassium Sodium Triglycerides Total protein Uric acid	Activated partial thromboplastin time Prothrombin time International normalized ratio	Bilirubin Blood Glucose Ketones Nitrite pH Protein Specific gravity Microscopy (if urinalysis is abnormal)

Abbreviations: ALT = alanine aminotransferase; AST = aspartate aminotransferase; CBC = complete blood count; RBC = red blood cell; WBC = white blood cell.

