** The clinical signs or symptoms associated with laboratory abnormalities might result in characterization of the laboratory abnormalities as Potentially Life Threatening (Grade 4). For example, a low sodium value that falls within a grade 3 parameter (125-129 mE/L) should be recorded as a grade 4 hyponatremia event if the subject had a new seizure associated with the low sodium value.

***ULN” is the upper limit of the normal range.

Hematology *	Mild (Grade 1)	Moderate (Grade 2)	Severe (Grade 3)	Potentially Life Threatening (Grade 4)
Hemoglobin (Female) - gm/dL	11.0 – 12.0	9.5 – 10.9	8.0 – 9.4	< 8.0
Hemoglobin (Female) change from baseline value - gm/dL	Any decrease – 1.5	1.6 – 2.0	2.1 – 5.0	> 5.0
Hemoglobin (Male) - gm/dL	12.5 – 13.5	10.5 – 12.4	8.5 – 10.4	< 8.5
Hemoglobin (Male) change from baseline value – gm/dL	Any decrease – 1.5	1.6 – 2.0	2.1 – 5.0	> 5.0
WBC Increase - cell/mm ³	10,800 – 15,000	15,001 – 20,000	20,001 – 25,000	> 25,000
WBC Decrease - cell/mm ³	2,500 – 3,500	1,500 – 2,499	1,000 – 1,499	< 1,000
Lymphocytes Decrease - cell/mm ³	750 – 1,000	500 – 749	250 – 499	< 250
Neutrophils Decrease - cell/mm ³	1,500 – 2,000	1,000 – 1,499	500 – 999	< 500
Eosinophils - cell/mm ³	650 – 1500	1501 - 5000	> 5000	Hypereosinophilic
Platelets Decreased - cell/mm ³	125,000 – 140,000	100,000 – 124,000	25,000 – 99,000	< 25,000
PT – increase by factor (prothrombin time)	1.0 – 1.10 x ULN **	1.11 – 1.20 x ULN	1.21 – 1.25 x ULN	> 1.25 ULN
PTT – increase by factor (partial thromboplastin time)	1.0 – 1.2 x ULN	1.21 – 1.4 x ULN	1.41 – 1.5 x ULN	> 1.5 x ULN
Fibrinogen increase - mg/dL	400 – 500	501 – 600	> 600	--
Fibrinogen decrease - mg/dL	150 – 200	125 – 149	100 – 124	< 100 or associated with gross bleeding or disseminated intravascular coagulation (DIC)

Source: [FDA 2007](#)

* The laboratory values provided in the tables serve as guidelines and are dependent upon institutional normal parameters. Institutional normal reference ranges should be provided to demonstrate that they are appropriate.

** “ULN” is the upper limit of the normal range.

Urine *	Mild (Grade 1)	Moderate (Grade 2)	Severe (Grade 3)	Potentially Life-Threatening (Grade 4)
Protein	Trace	1+	2+	Hospitalization or dialysis
Glucose	Trace	1+	2+	Hospitalization for hyperglycemia
Blood (microscopic) – red blood cells per high power field (rbc/hpf)	1 - 10	11 – 50	> 50 and/or gross blood	Hospitalization or packed red blood cells (PRBC) transfusion

Source: [FDA 2007](#)

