### 5.5 Visit Windows

Visit Windowing will not be applied. Summary tables or graphs will display scheduled visits and time points only; Unscheduled visits results will be listed, but not included in tables or graphs.

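### Laboratory tables hold scheduled visits only, so a worse value on an unscheduled recheck reaches no summary, and no table gives each participant's worst value or grade (minor)

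*SAP*

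**What the plan says.** SAP 3.1 counts change from baseline in clinical laboratory evaluations among the primary endpoints. Four rules decide how that part is summarised.

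- **Tables (SAP 6.6.2):** "The actual value and change from Baseline to each post-baseline evaluation will be summarized for each clinical laboratory parameter, including hematology and clinical chemistry". SAP 6.2.1 adds minimum and maximum to the statistics for continuous variables.
- **Unscheduled results (SAP 5.5):** no visit windowing is applied, and "Unscheduled visits results will be listed, but not included in tables or graphs".
- **Repeats (SAP 6.6.2):** "In the event of repeat values, the last non-missing value per study day/time will be used".
- **Abnormal values (SAP 6.6.2):** "A subset listing will be presented for all abnormal laboratory values". All laboratory data are listed as well.

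Protocol 9.4.2 specifies the same by-visit summaries and a participant listing of abnormal values, and leaves any further laboratory analysis to the SAP.

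On retesting, protocol 7.9 says that abnormal values which are unexpected or unexplained "may, at the discretion of the Investigator or Sponsor, be repeated as soon as possible until confirmed, explained, or resolved". It also says: "All clinical laboratory assays (hematology, chemistry, coagulation, and urinalysis) will be performed according to the central laboratory", following that laboratory's own procedures.

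Protocol Appendix 2 grades many laboratory parameters. The SAP uses the protocol scale only for adverse events, which "will be graded using the severity scale specified in the protocol" (SAP 6.6.1).

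**The concern.** A by-visit table answers what the values were at Day 28 or Day 84. It does not answer how bad a participant's worst result was, which is the usual question for laboratory safety. Here the by-visit tables also omit every unscheduled result, and an unscheduled result is often a recheck made because something looked abnormal. The maximum shown can therefore be lower than a participant's true worst post-baseline value, and a reader of the tables alone would not know.

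Protocol 2.5 names aPTT prolongation and increased WBC among the potential risks and also mentions a hepatic finding. Laboratory extremes are thus of direct interest in this first study in HAE.

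**Working it through.** No figure in the plan needs reproducing, so the check mainly traces the rules.

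**Step 1: where a worse recheck could arise.** Protocol 7.9 allows repeats of unexpected abnormal values. Because assays go to a central laboratory, a recheck would usually fall on a later, unscheduled day. That timing is an inference; no turnaround time is stated. Unscheduled HAE-attack visits are not a stated source: the blood samples listed for them in the schedule notes include no hematology, chemistry or coagulation. The only other unscheduled aPTT measurement found is after an overdose (protocol 6.5), which is not anticipated.

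**Step 2: where the recheck goes.** With no windowing it is not mapped to a scheduled visit, and SAP 5.5 keeps it out of tables and graphs. It reaches the full listing and, if abnormal, the abnormal-value listing. The scheduled value that prompted it stays in the by-visit table.

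**Step 3: whether another output picks it up.**
- The minimum and maximum cover scheduled visits only, one visit at a time.
- The AE tables generally do not. Protocol 8.2.1 counts a laboratory abnormality as an AE only if it has symptoms, needs intervention, or leads to interruption or discontinuation of study drug.
- Investigators judge the clinical significance of out-of-range values (protocol 7.9), but the SAP tabulates such an interpretation only for ECGs (SAP 6.6.4).
- Neither document plans a shift, worst-value, maximum-grade or threshold table for laboratory data.

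**Step 4: repeats in the same slot.** For two values at one study day/time, the table takes the last. It may be better or worse than the first, so the average effect is probably near zero.

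**Step 5: scale.** One affected participant as a share of a cohort:
- Cohort 1: 1/4 = 25.0%
- Cohort 2 or 3 at n = 6: 1/6 = 16.7%
- Cohort 2 or 3 at n = 12: 1/12 = 8.3%

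Scheduled post-baseline laboratory evaluations, from protocol Tables 1 to 3 and without the final safety visit whose day is redacted:
- Cohort 1, Days 7, 14, 28, 56, 84, 112, 140, 168: 8
- Cohort 2, Days 7, 14, 28, 56, 84, 90, 97, 111, 139, 167, 209, 251: 12
- Cohort 3, Days 7, 14, 28, 34, 41, 55, 83, 111, 153, 195: 10

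Rows per parameter in the full listing, scheduled results only:
- 16 participants: 4×8 + 6×12 + 6×10 = 32 + 72 + 60 = 164
- 28 participants: 4×8 + 12×12 + 12×10 = 32 + 144 + 120 = 296

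The abnormal-value listing is shorter.

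**Step 6: an illustration with assumed values.** The Appendix 2 row "PTT – increase by factor (partial thromboplastin time") sets Grade 1 at 1.0 to 1.2 × ULN and Grade 3 at 1.41 to 1.5 × ULN. Suppose a scheduled aPTT of 1.15 × ULN (Grade 1) and an unscheduled recheck of 1.45 × ULN (Grade 3). The table carries 1.15; the 1.45 appears only in listings. This shows the mechanism and is not an estimate. A moderate aPTT rise may also be regarded as expected and never rechecked, so aPTT may be less exposed than other parameters.

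**The case against.** The strongest reply is that the SAP delivers what protocol 9.4.2 specifies and adds a full listing. Additional analyses are optional there, so nothing promised is missing. The study is open-label and descriptive, with no formal hypothesis testing planned (SAP 6.2.1). Every value is listed, and with 4 to 12 participants per cohort the listings can be read in full. The Safety Review Committee reviews laboratory data for Cohort 1 and keeps ongoing oversight (protocol 4.2), and SAP 2.5 allows ad hoc safety analyses. This stands, and it is why the point is minor.

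It is also fair that the route depends on several conditions: the repeat is discretionary, it must fall on an unscheduled day, and it must be worse. Values picked out for being abnormal tend to be less extreme on repeat, so a worse recheck is the less likely direction. This stands too. Appendix 2 is meant to guide AE grading, calls its laboratory limits guidelines, and has two bilirubin scales, so a graded table needs some care.

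None of this closes the gap in reporting. Listings and committee review do not summarise the endpoint, and ad hoc analyses are not prespecified.

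A reader might infer that the plan hides adverse laboratory findings, or that the last-value rule biases the tables favourably. The documents do not support either. Unscheduled values are explicitly listed, and the last-value rule has no shown direction.

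**Conclusion.** The point holds as a minor improvement, not an error. Under SAP 5.5 and 6.6.2, a worse laboratory value on an unscheduled recheck enters no laboratory table, and no table gives a participant's worst value or grade. The tracing of the rules is firm. The consequence is not: the documents give no recheck rate, so no size can be derived, and the effect is zero if no recheck is worse than the value that prompted it. The percentages above show what one participant would represent, not how often this would happen. It would be wrong to conclude that safety data are lost or that the SAP departs from the protocol here.

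**What to change.** In SAP 6.6.2, add one summary by cohort of each participant's worst post-baseline value over scheduled, repeat and unscheduled results, and name it in SAP 5.5 as the exception to the scheduled-only rule.

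- Take the highest value for aPTT, PT/INR, ALT, AST and bilirubin, and both the highest and the lowest for WBC.
- Give the value, the multiple of ULN where applicable, and the Appendix 2 grade where one exists (INR has none).
- Grade bilirubin on the scale that matches the concurrent liver tests, and label all grades as guideline-based.

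Leave the by-visit tables and the last-value rule unchanged; the new table covers same-slot repeats because it takes the worst of them.

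The cost is one more table from data already collected, with a linked derivation for bilirubin. Protocol 9.4.2 already permits further laboratory analyses in the SAP, so no protocol amendment is needed. The downside is that laboratory figures may look slightly less favourable.
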